2. Feasibility of recruitment, enrollment, retention and adherence with a two-arm pilot RCT (WhatsApp and control). A target retention rate of at least 90% completing the pilot trial is sought. Retention will be measured by the proportion of participants who will remain in the study by the end of the follow-up period. If we are unable to achieve this target, alternative strategies will be considered for the UH3 phase. One of the primary objectives is to estimate the proportion of successful return blood donation for planning the programmatic randomized clinical trial in the UH3 phase.
3. Acceptability will be assessed with quantitative surveys and participant focus groups to understand the opinions and perspectives of acceptability, effectiveness, feasibility and cultural appropriateness of the docu-drama, WhatsApp and control communication interventions.

Secondary Objectives

To design culturally appropriate communication interventions: docu-drama and WhatsApp groups for retaining first-time blood donors using the PRECEDE-PROCEED framework.

To examine intervention-specific increases in knowledge, attitudes, beliefs, motivations, intention, and relatedness as potential mediators of intention to donate among first-time blood donors. Evaluate the reliability of new or modified outcome measurement instruments.

Study Design

The pilot study utilizes a mixed-methods approach to develop a novel docu-drama communication strategy, evaluate the feasibility of a larger pragmatic randomized controlled trial (RCT) of a WhatsApp based communication strategy and assess acceptability of the communication strategy aimed to increase blood donation among first time blood donors within the catchment areas of the SZBC.

There are two communication interventions: docu-drama and WhatsApp. However, because the development of the docu-drama takes more time, it will not be feasible to include the docu-drama intervention in the pilot RCT, recruit 100% participants, follow up for 6-months for the primary outcome and evaluate the secondary outcomes, considering the duration the UG3 phase. Therefore, only the WhatsApp intervention will be piloted in the RCT. The docu-drama intervention will be designed and test-run in preparation for an RCT in the UH3 phase.

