- Intervention relatedness

Several measures are new or adapted: cultural appropriateness, acceptability, feasibility, perceived usefulness and perceived ease of use. These measures will be assessed for reliability.

The secondary outcomes will be determined through the use of questionnaires.

Sample Size Assumptions

Docu-drama design sample size

The planning of the docu-drama will involve participants who will take part in the drama design workshop discussion (n=20). In addition, we will recruit n=10 first-time donors to test-run and provide feedback on the newly designed docu-drama intervention.

WhatsApp intervention sample size

Key informant interviews (n=24) will help the team to identify how the WhatsApp platform will be used, and the WhatsApp intervention.

Pilot RCT sample size

The targeted sample size is 64 first time blood donors per treatment arm.

One of the primary objectives is to estimate the proportion of return blood donation for planning the randomized clinical trial in the UH3 phase. As the donor return rates are unknown given the Covid-19 pandemic, we focused on obtaining an acceptable precision of event rates for the sample size and power calculation for the UG3 phase. Figure 6 presents the sample size needed to achieve 80% confidence interval length equal to 0.15, 0.20, and 0.25 using the Exact (Clopper-Pearson) method, assuming the return rate ranging from 5% to 30% (Fleiss et al., 2003, Newcombe et al., 1998). A sample size of 59 produces a two-sided 80% confidence interval with a width equal to 0.149 when the sample proportion is 20%, which is the targeted donor return rate in the WhatsApp group. Considering 10% lost-to-follow-up, we would need a sample size of 64 for each treatment arm.

Alternatively, Figure 7 presents the minimum donor return rate in the WhatsApp group that can be significantly detected under various effective sample sizes and event rates in the control group. For example, if the donor return rate in the control group is 3%, an effective sample size of 59 in each group achieve 80% power to detect a minimum difference of 17.21% (i.e. the donor return rate in the WhatsApp group = 20.21%) when using the two-sided Fisher's exact test, with a 2-sided Type I error rate of 5%.

[figure not shown]

Figure 6: Sample size calculation based on precision

[figure not shown]

Figure 7: Alternative sample size calculation

Schedule of Assessments: Follow-Up

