The participants will be invited to participate in screening after blood donation at SZBC sites.

Table 1: Schedule of assessments for pilot RCT

Assessment	Screening (At first-time donation)	Baseline A pre- randomization (Day 0)	Baseline B post- randomization (Day 0)	6-month follow-up (Days 176- 190) ¹	6-12 months follow-up
Informed Consent Form	X				
Demographics	X				
Blood donation attitudes, subjective norms, perceived behavioural control, and intention		X		X	
Randomization			X		
Intention of using the intervention			X		
Acceptability of the intervention			X	X	
Feasibility of the intervention			X	X	
Cultural appropriateness of the intervention			X	X	
Perceived usefulness of the intervention			X	X	
Perceived ease of use of the intervention			X	X	
Intervention relatedness			X	X	
Return blood donation attempts ²				X	
Focus groups of participant views of acceptability, effectiveness, feasibility, and cultural appropriateness					X
Note: The participants involved in the test-run of the docu-drama will be surveyed prior-to and after the docu-drama with all instruments (except blood donation attempts) and participate in facilitator-led focus groups.					
¹ 6-months with a 2-week window.					
² Donor return will be assessed via telephone calls and cross-checked with SZBC donor records.					

Follow-up assessments for the pilot RCT

There will be two follow-up assessments.

6 months

The 6-month assessment for the pilot RCT will occur over the phone with a 2-week window of the 6-month pilot. Donor return will be assessed via telephone calls and cross-checked with SZBC donor records. The six-month follow-up will repeat baseline post-randomization questionnaires and include the intention of using the intervention, acceptability of the intervention, feasibility of the intervention, cultural appropriateness of the intervention, perceived ease of use of the intervention, perceived usefulness of the intervention, and intervention relatedness. In line with definitions of acceptability, appropriateness and feasibility given by Weiner et al. (2017), we defined these characteristics as follows:

Acceptability is the perception among first-time blood donors that an intervention is agreeable or satisfactory for promoting blood donation. Thus, acceptability will be measured with a five-item questionnaire.

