5. Mapping and interpretation: The research team will analyse key characteristics as laid out in the charts and generate a schematic diagram of the key themes. This will include creating typologies, finding associations, providing explanations, and developing strategies.

Data will be coded and analyzed for themes using the Qualitative Software and Research (QSR) Nvivo Release 1.0 (Released March 18, 2020).

Information from the different qualitative methods will be linked to the focus of the study as follows:

1. **Key informant interviews:** These will be used to get information that will help the research team to identify challenges and motivations for first-time blood donors to repeat donation among respondents. The information will help in creating the study interventions.
2. **Design workshop:** Information from the design workshop will be used to create a design document to guide the scriptwriter to produce a script that truly captures the focus of the drama intervention.
3. **Focus group discussions:** Information from the focus groups will be used to identify what worked and what did not work well for the interventions, and to assess the acceptability, *feasibility and cultural appropriateness of the interventions.*

Quantitative Data Analysis

Statistical analysis will be completed using SAS or R.

Analysis pilot trial:

The analysis for the pilot study is to inform the planned larger UH3 randomized controlled trial and will follow the same anticipated primary analysis (see below) with acknowledgment of low power to evaluate effectiveness.

The feasibility of the larger study will be assessed with descriptive statistics for enrollment rates, retention, and adherence. Key blood donation measures needed to inform the design of the larger UH3 randomized controlled study will be analyzed and include the proportion of participants who return to the blood centre to donate blood.

Primary analysis (anticipated) for the larger UH3 randomized controlled trial:

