Baseline characteristics and outcome variables of each group will be summarized by proportions for categorical variables and means with standard deviations for continuous variables as appropriate. The primary analysis will be performed as ‘intent-to-treat’ with all enrolled subjects included in the analysis as randomly allocated regardless of actual compliance. All analyses will account for stratification by blood donor type. The primary analysis will use logistic regression with a two-sided type I error of 5% using robust standard

errors. Secondary analyses are not adjusted for known multiplicities (e.g., multiple secondary endpoint assessment). As such, all secondary analyses will intentionally not focus on conclusions around the statistical significance, but rather on practical or clinical benefit. Each additional outcome measure will be analyzed separately by appropriate generalized linear regression models (e.g., logistic regression models for binary outcomes and linear models for continuous outcomes) in a similar way to the primary analysis using robust standard errors.

Subgroup analyses for the primary endpoint and major secondary outcomes will be performed to determine whether the intervention differs qualitatively across various baseline-defined subgroups. Subgroup analyses will be performed by age, gender, blood donation group, and blood donation type (e.g., voluntary non-remunerated, family/replacement blood donors). An overall test of heterogeneity will provide evidence of whether the magnitude of the estimates varies across these baseline subgroups.

If necessary, missing data will be handled by multiple imputation via chained equations (MICE), as implemented in SAS PROC MI procedure (White et al., 2011).

Quality Assurance

A Data Safety Monitoring Board (DSMB) will provide independent monitoring of this pilot study in accordance with the BLOODSAFE DSMB charter. The DSMB will have an opportunity to review the protocol and informed consent and provide feedback prior to study initiation. An open report will be prepared by a DCC statistician, and a closed report will be generated by statisticians from the DCC. Interim data summaries will be prepared by the DCC statisticians and reviewed at regular intervals by the DSMB (at least twice a year). **The DSMB is an oversight committee assigned by the National Institutes of Health (NIH) to oversee the conduct of the study.**

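### The pilot's arm comparison has no rule for an arm with no return attempts; read as a robust Wald test, it rejects too often when both arms return below about 6%

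*Combined protocol and SAP*

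**What the plan says.** Under Data Analysis, the paragraph on the pilot trial says its analysis "will follow the same anticipated primary analysis (see below) with acknowledgment of low power to evaluate effectiveness". The primary analysis described next is this: "The primary analysis will use logistic regression with a two-sided type I error of 5% using robust standard" errors. It is by intention to treat, with "all enrolled subjects included in the analysis as randomly allocated regardless of actual compliance", and accounts for donor type. The software is SAS or R. No test statistic (Wald, score or likelihood ratio) is named, and no passage covers an arm with no return attempts.

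The pilot sample size section plans 64 donors per arm and an effective 59. Its power example reads "if the donor return rate in the control group is 3%, an effective sample size of 59 in each group achieve 80% power". The WhatsApp rate in that example is 20.21%, tested with a two-sided Fisher's exact test. Fisher's test appears only there. The precision calculation is made "assuming the return rate ranging from 5% to 30" per cent. The Background cites a 3.1% return rate among first-time donors in a Ghanaian study.

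The primary outcome, under Outcome measures, is the proportion of return attempts in each arm.

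**The concern.** At rates near 3%, an arm of about 60 donors can easily have no events. Logistic regression then has no finite maximum-likelihood estimate of the arm effect. With model-based standard errors the Wald test fails safely, because the standard error diverges too. With the robust standard errors that the plan specifies, it does not. The acknowledged low power is a warning about false negatives, whereas the risk here is false positives.

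At stake are the between-arm p-value, odds ratio and interval that are meant to inform UH3. If WhatsApp does little and return stays very low, one attempt against none could come out as significant with an unbounded odds ratio. A remedy chosen after seeing the empty arm would be data-driven.

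**Working it through.** **Inputs.** Two-sided 5%, logistic regression, robust standard errors (primary analysis section). 64 enrolled and 59 effective per arm, 3% control, 20.21% WhatsApp, planned range 5–30% (sample size section).

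**1. The plan's own figures.** The 80% Clopper–Pearson width at n=59 and a proportion of 20% comes to 0.149, as stated. Enumerating Fisher's exact test over both binomials for 3% versus 20.21% at n=59 gives power of 79.98%, against the stated 80%.

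**2. One empty arm.** In the two-arm model the log odds ratio is ln[x₁/(n−x₁)] − ln[x₀/(n−x₀)], which diverges when x₀=0. The robust variance is the sum over arms of Σ(residual²)/[n·p̂(1−p̂)]².

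- Non-empty arm: this equals 1/x + 1/(n−x).
- Empty arm: the numerator is n·p̂², so the term is 1/[n(1−p̂)²], which tends to 1/n as p̂ tends to 0.
- For 0/64 versus 1/64: 1/1 + 1/63 + 1/64 = 1.0315, so SE = √1.0315 ≈ 1.016.

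The model-based term for the empty arm, 1/[n·p̂(1−p̂)], goes to infinity instead.

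Fitting this table by Newton steps gives p=0.22 at 4 iterations, 0.042 at 5 (coefficient 2.06, SE 1.01), below 1e-6 from 8, and 4e-12 at 10. Default R glm reports convergence with coefficient 17.4 and robust SE 1.01. A Python GLM gives 20.4 and 1.01; its model-based SE is about 16,000 (p=0.999). A fully iterated robust Wald test therefore rejects every table with exactly one empty arm.

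**3. Type I error with both arms at rate p.** Let q=(1−p)ⁿ be the chance that one arm is empty. Then type I error = 2q(1−q) + P(both arms non-empty and the test rejects).

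- n=64, 3%: q=0.1424; 2×0.1424×0.8576=24.42%; plus 0.04% gives 24.46%.
- n=59, 3%: q=0.1658; 2×0.1658×0.8342=27.66%; plus 0.03% gives 27.69%.

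Exact enumeration, n=64 / n=59. The last column uses robust Wald, but Firth with a penalised likelihood-ratio test if an arm is empty:

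| Common rate | Robust Wald | Firth fallback |
|---|---|---|
| 3% | 24.5% / 27.7% | 1.3% / 1.1% |
| 5% | 7.8% / 9.6% | 2.2% / 2.1% |
| 10% | 3.5% / 3.2% | 3.4% / 3.1% |
| 20% | 4.8% / 4.6% | 4.8% / 4.6% |

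The Wald figure crosses 5% at a common rate of 5.9% / 6.4%. From 6.5% to 30% its maximum is 4.82% / 4.78%.

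**4. Donor type in the model.** By simulation at 3%, Wald type I error is 24.6% / 28.2% (20,000 trials per setting; strata split by the 47% voluntary share given for all blood collected, which is an assumption for first-time donors). With a 50:50 split it is 24.7% / 27.3% (6,000 trials). Adjustment does not remove the problem.

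**5. When the arms differ.** With control at 3%, the probability that an arm is empty, Wald rejects and Firth does not is 13.7% / 16.8% if WhatsApp returns at 5%, 3.2% / 4.9% at 10%, and 0.03% / 0.07% at 20.21%.

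**6. The remedy.** Firth p-values for 0 versus 1, 4 and 5 events at n=64 are 0.466, 0.051 and 0.024. The fallback's maximum type I error over 0.5–30% is 4.82% / 4.77%. Its power at 3% versus 20.21% is 87.6% / 83.7% (87.6% / 84.5% with donor type in the model).

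**The case against.** **The test is not named.** This stands: Wald is an inference, though the usual one when robust standard errors are specified. A robust score test of the same model gives p=0.315 for 0 versus 1 and type I error of 3.8% / 3.5% at 3%. A reader might infer that the plan commits to a test with 25% type I error. It does not; it leaves the choice open, and one natural choice behaves that way.

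**An analyst would notice.** Partly true. One Python logit routine flags non-convergence, and the per-group proportions would show 0/64 beside the p-value. But default R glm reports convergence, and the plan does not say what to do next.

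**Both arms at 3% is extreme.** It lies below the planned precision range, and 3% is offered only as an example. The 3.1% counts donors who returned to give blood, whereas the pilot counts attempts, including failed ones, and its controls receive a reminder call. The documents therefore do not show that the pilot will fall in this region. Even so, 5%, the bottom of the planned range, is affected.

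**The consequence is small.** Largely right. A reader might infer that the primary outcome or the decision to proceed to UH3 is compromised. The primary outcome is a per-arm proportion, which needs no model. The only stated trigger for change is the 90% retention target: "If we are unable to achieve this target, alternative strategies will be considered for the UH3 phase".

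**A Fisher fallback would be simpler.** At n=64 it matches the Firth fallback's power (87.6%), with type I error of 0.4% at 3%. But a single Fisher table ignores donor type, which the plan says all analyses will account for.

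**Conclusion.** The point holds as a gap in the plan of minor-to-moderate weight. If the comparison is a fully iterated robust Wald test, and the diverged fit is accepted, type I error with equal rates is 24.5% (n=64) or 27.7% (n=59) at 3%, and 7.8% or 9.6% at 5%. The excess is confined to common rates below about 6–6.5%, and at 3% nearly all of it comes from trials with exactly one empty arm.

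It would be too strong to say that the test keeps its level at every higher rate. It does up to 30%, the top of the planned range; above that it slightly exceeds 5% in places (5.13% at 40%, n=64), for reasons unrelated to empty arms. At the planned effect the problem practically vanishes.

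**What to change.** Add to the pilot analysis text:

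- The arm comparison uses logistic regression with arm and donor type, and a Wald test with robust standard errors.
- If either arm has no observed return attempts, Firth-penalised logistic regression with the same terms is used instead, with a penalised profile-likelihood p-value and interval.

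Firth throughout is an acceptable alternative if fixed in advance. Its type I error is also at most 4.82% / 4.77% for rates of 0.5–30%, and its power is higher (89.8% / 86.7% at 3% versus 20.21%), but it departs from the model anticipated for UH3. Either way, one rule should be set before outcome data are seen.

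No special imputation rule is needed for this. Imputation is planned only if necessary, and should seldom be needed for this outcome: "Donor return will be assessed via telephone calls and cross-checked with SZBC donor records".

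The cost is a few sentences. Firth is available in SAS and R, and sample size, data collection and the UH3 model do not change. The downside is conservatism at very low rates: unadjusted type I error is 1.1–1.3% at 3%, and at least 5 events against none are needed to reject.

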A docu-drama group of purposively selected 10 first-time donors will be formed. They will attend one meeting to watch two docu-dramas, each lasting 15 minutes, followed by a one-hour focus group discussion on the content of the drama, and feasibility, acceptability and cultural appropriateness of the intervention. Prior to, and after the viewing and discussion, a pre-, and post-test survey on the theory of planned behaviour constructs and implementation research measures will be conducted. Two study team members will facilitate the discussions. The docu-drama test-run will include an attendance list at the scheduled meeting. Those who attended, watch the 2 episodes, and stayed for the discussion will be considered as having adhered to the intervention.

The PROCEED Component will be addressed during the four years of the UH3 phase.

The PROCEED component involves exposing the interventions to participants and evaluating their outcomes. The UG3 pilot RCT will address the feasibility and inform the design of the PROCEED component.

The Theory of Planned Behaviour

As shown in Figure 4, according to the theory of planned behaviour, behavioural intention to return to donate in 6 months is influenced by factors such as attitude, subject norms, and perceived behavioural control, and has been examined in first-time blood donors (Masser et al., 2012). The theory of planned behaviour model will be used to evaluate the effect of intervention-specific changes in attitude, subject norms, and perceived behavioural control on intention to return to donate blood, and on actual return donation attempt.

[figure not shown]

Figure 3: Theory of planned behaviour

The Technology Acceptance Model

As shown in Figure 5, according to the technology acceptance model, intention to use technology (in this case, WhatsApp) is influenced by perceived usefulness and perceived ease of use of the technology (Venkatesh & Bala, 2008).

[figure not shown]

Figure 4: Technology Acceptance Model

Randomization

The docu-drama design and test-run will not employ randomization. The participants enrolled in the pilot RCT will be randomized immediately following the baseline assessment with a 1:1 allocation ratio to WhatsApp or control using blocked randomization (with randomly mixed

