A major assumption is that there will be high fidelity of the interventions. We will assess adherence to the interventions as a key element of fidelity (Carroll et al., 2007). Adherence will include subcategories of content, frequency, duration and dose (Carroll et al., 2007). The extent to which the intended content or frequency of WhatsApp and docu-drama are implemented will

represent the degree of implementation fidelity achieved for the two interventions (Carroll et al., 2007; Song et al., 2010).

Study Population

Inclusion Criteria

Docu-drama design

Design workshop participants will be drawn from blood donors, non-blood donors, drama experts, drama actors, and communication professionals. All must be at least 18 years old, consent to participate and understand English.

WhatsApp intervention design

Key informants will be drawn from the NBSG staff, community-based blood donation volunteers, blood donors, and non-blood donors. All must be at least 18 years old, consent to participate, and understand one of English, Twi, or Ga.

Pilot RCT

- At least 18 years-old
- First-time whole blood donor with the SZBC of the NBSG
- Eligible to donate again
- Consent to participate
- Understands one of English, Twi, or Ga
- Have a smart phone
- Have, or be willing to sign up for an active WhatsApp account

Docu-drama test-run

- At least 18 years-old
- First-time whole blood donor with the SZBC of the NBSG
- Eligible to donate again
- Consent to participate
- Understands one of English, Twi, or Ga

Exclusion Criteria

Docu-drama design

Do not meet the above inclusion criteria

WhatsApp intervention design

Do not meet the above inclusion criteria

Pilot RCT

History of more than one lifetime whole blood donation (with any blood centre)

Docu-drama test-run

History of more than one lifetime whole blood donation (with any blood centre)

Outcome measures

Primary Outcome

The primary outcome for the pilot RCT is to estimate the proportion of return blood donation attempts within six months of enrollment for each arm.

Secondary Outcomes

The secondary outcomes are the following measures.

WhatsApp and control

- Blood donation attitudes,
- subjective norms,
- perceived behavioural control,
- intention,
- ease of use of WhatsApp,
- perceived usefulness of WhatsApp.

Docu-drama, WhatsApp and control

- Intention of using the intervention

- Acceptability of the intervention
- Feasibility of the intervention
- Cultural appropriateness of the intervention

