E. Demographics (continued)

12. What is your ethnic background?

- 1 Akan
- 2 Ewe
- 3 Dagbani
- 4 Ga/Dangbe
- 5 Hausa
- 6 Other, specify: _____

13. Do you belong to a religious faith?

- 1 Yes, Christian
- 2 Yes, Moslem
- 3 Yes, Traditionalist
- 4 Yes, Other, specify: _____
- 5 No

Signature: _____ Date: _____

16. Participation Withdrawal Form

Withdrawal

Participant ID:

Date of withdrawal:

(example: 01-APR-2021)

- - 0 2

Day

Month

Year

Participant
3-letter code:

Bloodsafe Logo
Placeholder

Site:

01 Korle-Bu Bld Bank
02 Korle-Bu Maternity
03 Pentecost Hospital
04 LEKMA Hospital
05 Maamobi Polyclinic
06 Accra Shopping Mall
07 Mobile Unit

Complete this form if a participant has actively (verbally or in writing) withdrawn consent or if the participant is withdrawn by the PI from the C-CAD study.

A. Withdrawal

1. Indicate the type of withdrawal (mark only one):

- 1 Participant actively withdrew consent from all aspects of the C-CAD study
2 Administrative withdrawal

2. The participant requested destruction of the following (mark all that apply):

- 1 All participant recordings
2 All participant data
3 N/A (The participant did not request destruction of data or recordings)

3. Reason for withdrawal:

- 1 Participant preference
2 Staff/PI request
3 IRB/sponsor request
4 Other; specify: _____

Staff person completing this form (please print): _____

Signature: _____

Signature indicates a withdrawal has been verified with site and all necessary documentation is available.

17. SOP: Randomizing participants into study groups for the pilot RCT of WhatsApp and control

BLOODSAFE: Standard Operating Procedure

Randomizing participants into study groups for the pilot RCT of WhatsApp and control		Version 0.3 15 Feb 2021
---	--	-----------------------------------

Revision history		
Version	Date	Description

1. Purpose

The purpose of this standard operating procedure (SOP) is to describe how to use the randomization application for the pilot RCT of WhatsApp and control for the *Community-Based Communication Approaches for Blood Donation in Ghana-Pilot Study* (C-CAD) study. Participants are allocated with a 1:1 ratio to WhatsApp or control stratified by one of two donor types (e.g., Voluntary non-remunerated donor or Family/replacement donor) using the web-based application described in this SOP. Participants will be randomized after the consent and screening process immediately following completion of Baseline A case report form (CRF).

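### The Month 6 comparison of attitude, subjective norms, perceived behavioural control and intention does not name the pre-randomization Baseline A score as a covariate, so available precision may go unused

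*Combined protocol and SAP*

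**What the plan says.** Under Data Analysis, Quantitative Data Analysis, the paragraph on the pilot trial says that its analysis "will follow the same anticipated primary analysis (see below) with acknowledgment of low power to evaluate effectiveness". The text that follows, headed as the anticipated primary analysis for the UH3 trial, sets a logistic regression with robust standard errors and adds: "All analyses will account for stratification by blood donor type". Each further outcome is then analysed separately with a suitable generalized linear model, for example "linear models for continuous outcomes) in a similar way to the primary analysis using robust standard errors". No other covariate is named, no change score is defined and no repeated-measures model is given.

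The Secondary Outcomes list for WhatsApp and control includes attitudes, subjective norms, perceived behavioural control and intention. Table 1 has a row for "Blood donation attitudes, subjective norms, perceived behavioural control, and intention", marked at Baseline A (pre-randomization, Day 0) and at the 6-month follow-up. The Baseline A and Month 6 case report forms (Study Tools 6 and 10) carry the same items for these scales: 6 for attitude, 6 for norms, 5 for control and 3 for intention. The randomization SOP (Study Tools 17) has randomization follow immediately after the Baseline A form is completed.

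**The concern.** The primary outcome, a return donation attempt within six months, has no baseline value. A model built like the primary one therefore has no baseline term to copy: read literally, it contains arm and donor type. The four scales do have a baseline value, taken before allocation and so a valid covariate.

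Two things are at stake. If the baseline score predicts the Month 6 score, leaving it out makes the interval for the arm difference wider than it need be. And any chance difference between the arms at baseline passes in part into the Month 6 comparison. The plan says that secondary analyses will look to practical benefit rather than significance, so the estimate and its interval are the whole product for these outcomes.

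**Working it through.** **Inputs from the documents.** 64 donors per arm, 1:1 allocation, 10% loss to follow-up, an effective size of 59 per arm in the sample-size text.

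**The plan's own figures.** At n = 59 and a 20% return rate, the 80% Clopper-Pearson width computes to 0.1490 (stated 0.149). The two-sided Fisher exact power for 3% against 20.21% computes to 0.7998 (stated 80%). Both reproduce, and both concern the binary return outcome. No precision or power is stated for the four scales. With 10% loss, 64 × 0.9 = 57.6, taken below as 58 evaluable per arm.

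**Assumptions.** The outcome is in SD units (SD = 1 within donor type). The correlation ρ between Baseline A and Month 6 scores within donor type is not in the documents; the range 0.3 to 0.7 is shown.

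**Formulas.** SE of the arm difference = √(2/58 × k), with
- k = 1 for Month 6 scores without the baseline score;
- k = 1 − ρ² with the baseline score as covariate;
- k = 2(1 − ρ) for a change score.

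Equivalent size per arm under adjustment = 58/(1 − ρ²).

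| | ρ = 0.3 | ρ = 0.5 | ρ = 0.7 |
|---|---|---|---|
| SE, Month 6 only | 0.186 | 0.186 | 0.186 |
| SE, change score | 0.220 | 0.186 | 0.144 |
| SE, baseline-adjusted | 0.177 | 0.161 | 0.133 |
| Variance reduction, adjusted against Month 6 only | 9% | 25% | 49% |
| Equivalent donors per arm | 64 | 77 | 114 |

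Worked case at ρ = 0.5: √(2/58) = 0.186; √(2/58 × 0.75) = 0.161; 58/0.75 = 77.

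**Check by simulation.** In 5,000 simulated trials with 59 per arm, the ratio of adjusted to unadjusted SE was 0.957, 0.866 and 0.717 at ρ = 0.3, 0.5 and 0.7. Theory, √(1 − ρ²), gives 0.954, 0.866 and 0.714. At ρ = 0 the ratio was 1.004, so adjusting for an uninformative score costs almost nothing.

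**Chance imbalance.** The SE of a baseline difference between arms is also 0.186 SD. An imbalance above 0.2 SD in either direction on a given scale then has probability P(|Z| > 0.2/0.186), about 28%. At ρ = 0.5, a 0.2 SD imbalance moves the Month 6-only estimate by 0.5 × 0.2 = 0.1 SD in the same direction, and a change-score estimate by 0.1 − 0.2 = −0.1 SD. Adjustment removes this shift.

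**The case against.** The strongest reply is that the plan is silent rather than wrong. It promises appropriate models built in a similar way to the primary one and gives no complete covariate list, so a linear model that includes the baseline score would be consistent with it. That stands: a reader might infer that the plan has decided against baseline adjustment, and the text does not support that.

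A reader might also infer that a change-score comparison is intended, because the theory of planned behaviour section aims to "evaluate the effect of intervention-specific changes in attitude, subject norms, and perceived behavioural control on intention to return to donate blood" and a secondary objective speaks of increases. Those passages concern mediators of intention and of return. They do not describe the comparison of arms, so no change-score analysis can be read out of them. The change-score row above shows only that such an analysis would not be a better substitute.

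A further reading would extend the point to knowledge and beliefs, which are also on both forms. They are not in the Secondary Outcomes list, and no total score is defined for them.

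The size is also open. ρ is assumed, and what counts is the correlation remaining after donor type. Two features could lower it. The items ask about the next four months, which at baseline nearly coincides with the four-month wait before a second donation but at Month 6 lies beyond it. And baseline is taken at the donation visit, Month 6 by telephone. At ρ = 0.3 the gain is modest.

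Finally, these are secondary outcomes of a pilot that concedes low power, and the model text sits under the UH3 heading, so carrying it to the pilot's secondary scores takes a short inference. This limits the weight of the point. It does not remove it, because nothing in the documents puts the baseline score into the arm comparison.

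**Conclusion.** The point holds as an unstated covariate with a cost in precision, not as an error of validity. A reader who concluded that the secondary comparisons are biased would go too far: randomization protects them on average. As written, the only covariate named for the four scales is donor type, and the pre-randomization score of the same scale is not mentioned.

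Using that score lowers the variance of the arm difference by about 9% to 49% over the assumed range of ρ, with 25% at ρ = 0.5. These figures rest on 58 evaluable donors per arm and on a correlation within donor type that the documents do not supply. The direction is firm for any ρ of more than trivial size. A flat claim that a large share of the sample is lost would not be supported, since at ρ = 0.3 the equivalent size is 64 against 58. This is a free improvement of moderate to low weight.

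**What to change.** Add to the Quantitative Data Analysis text, after the sentence on additional outcome measures:

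> *Month 6 attitude, subjective norms, perceived behavioural control and intention scores will be compared between arms by linear regression on arm, donor type and the participant's Baseline A score of the same scale, with robust standard errors.*

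Limit this to the four listed secondary outcomes. The same model can serve knowledge and beliefs only if they are to be compared between arms and a score is first defined. Do not extend it to the Baseline B scales (acceptability, feasibility, cultural appropriateness, usefulness, ease of use, relatedness). They are first measured after randomization, when participants may already know their arm, and are not clean baseline covariates.

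The cost is one sentence. No new data, visits or participants are needed, and the same wording can carry into the UH3 plan.
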